- Note: patients with asymptomatic low volume locoregional recurrent disease will be allowed to enroll on this study after discussion with the PI. In the case where the low volume recurrence is amenable to SBRT, it will be included in the SBRT treatment. In the case where the low volume recurrence is not amenable to SBRT based on reirradiation risk, then we will follow these lesions with re-imaging scans and reassess at later time points for further local control. Additionally, if these patients fail only at the untreated site (due to the untreated recurrence/disease not being amenable to SBRT) they will be censored in the primary efficacy analysis at that time.

__12. Does not have castration resistant disease

- Castration resistance defined as progression of disease despite serum testosterone level of <50 ng/dL

__13. PSA \geq 0.2 prior to start of androgen deprivation treatment

PSA value:

Date:

__14. Patients will be receiving approximately 36 weeks of ADT as part of this trial. The 36 weeks of ADT may start prior to consenting to this study. The patient may join the study at any point of the 36-week period of ADT treatment.

- Only Luteinizing hormone-releasing hormone (LHRH) agonist/antagonist treatment is considered ADT; bicalutamide or other antiandrogens used alone do not count.

Patient MRN	Patient Initials (F, M, L):
-------------	-----------------------------

___15. Patients must be willing to receive bisphosphonate or RANKL inhibitor bone health agents at the dose and schedule consistent with the treatment of bone metastases or prevention of osteoporosis, starting approximately from when the patient begins protocol therapy, until the patient's testosterone reaches normal levels or at the discretion of the PI. Patients who are already on a bone health agent separate from the protocol may continue on this treatment regimen and will not be required to start treatment with an additional bone health agent.

___16. Patients may have received prior hormone therapy at the discretion of the PI. Patients may have received prior targeted therapy in the context of definitive therapy.

___17. Patients may have had one prior systemic non-chemotherapeutic treatment (i.e. immunotherapy, receptor tyrosine kinase inhibitor, antiangiogenic agent, differentiating agent) for recurrent or metastatic disease.

___18. Must have refused standard of care treatment for metastatic disease

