5.2 Cycle Definition

In the absence of delay due to toxicity, each treatment cycle lasts 28 days.

Cycle 1 Day 1 is defined by the administration of SBRT.

Cycles 2-7 Day 1 is defined by the administration of radium Ra 223 dichloride.

Post Ra-223 is defined as approximately 28 days post-last dose of radium Ra 223 dichloride.

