5.3 Treatment Plan

The treatment plan is as follows ([Table 5.3](#)). Participants must already have received at least 28 days of ADT (leuprolide OR goserelin OR degarelix OR relugolix) **prior** to initiating Cycle 1 Day 1 SBRT. While on protocol therapy, participants must also receive bisphosphonate or RANKL inhibitor bone health agents at the dose and schedule consistent with the treatment of bone metastases or prevention of osteoporosis, until their testosterone levels reach the normal range or at the discretion of the PI.

Stopping rules may be implemented if there is unacceptable toxicity. For further details see [Section 13.0](#)

Table 5.3 Treatment Regimen and Schedule

Agent/Therapy and Route of Administration	Dose	Timing of administration and planned duration
Stereotactic Body Radiation Therapy (SBRT) via External Beam Radiation via TrueBeam Stx	9Gy x 3 fractions (bone) 5Gy x 5 fractions (lymph node) 10Gyx5 (lung)	Cycle 1 Day 1, then dosing administered minimum every 40 hours over 7 to 21 days during Cycle 1
Radium Ra 223 dichloride via Slow IV over 1 minute	55 kBq/kg	Cycles 2-7 Day 1 of each 28-day cycle
Leuprolide OR goserelin OR degarelix OR relugolix Per package insert/investigator discretion		Starting at least 4 weeks prior to SBRT and continuing for a total of 36 weeks as part of regimen on protocol

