11.0 STUDY CALENDAR

All procedures may increase in frequency if clinically indicated.

Table 11.0 Study Activity Calendar

Protocol Activities*	Screening ^a	Protocol Therapy ^{c, d}				Follow-up (Max. 5 years)	
		Cycle 1	Cycle 2	Cycle 3-7	Post Ra-223/EOT ⁱ	Response ^j	Long-term ^k
		Day 1 ^{e,f}	Day 1 ^{g,h}	Day 1 ^g			
Informed Consent ^l	X						
Medical History ^m	X						
Eligibility ⁿ	X						
Registration ^o	X						
Physical Exam ^p and Vital Signs ^q	X	X	X	X	X	X	
Height	X						
ECOG (Appx. A)	X	X	X	X	X	X	
Con-medications ^r	X	X	X	X	X	X	
AE assessment ^s		x ^t	x ^t	x ^t	x ^t	x ^u	x ^u
12-lead EKG	x ^v						
CBC with differential	X	X	X	X	X	X	
Serum chemistry ^w	X	X	X	X	X	X	
Prostate-specific antigen (PSA)	x ^b	X	X	X	X	X	
Serum testosterone	x ^b	X	X	X	X	X	
Immune-biomarker studies ^x		X	X		X		
Archival tumor tissue ^y	X						
Fresh tumor tissue ^z	X						
Tumor Evaluation ^{aa}	X				X	x ^{bb}	
ADT: Leuprolide OR goserelin OR degarelix OR relugolix ^{dd}	Dosing per package insert/ physician discretion for 36 weeks starting at least 28 days prior to SBRT						
Criteria to initiate stereotactic body radiation therapy (SBRT)		x ^f					
SBRT ^{f, cc}		X					
Criteria to initiate radium Ra 223 dichloride			x ^h				
Radium Ra 223 dichloride ^{h, cc}			Day 1 of each cycle				
Survival ^k							X

* Participants will receive bisphosphonate or RANKL inhibitor bone health agents at the dose and schedule consistent with the treatment of bone metastases or prevention of osteoporosis, starting approximately when protocol therapy begins until the participant's testosterone reaches normal levels (>50 ng/dL) or at the discretion of the PI.

a. Screening activities to occur within 56 days prior to Cycle 1 Day 1 of protocol therapy **except** PSA and serum testosterone.

- b. Screening PSA and serum testosterone should occur prior to 1st dose of androgen deprivation therapy (ADT). If not drawn prior to starting ADT, this will not constitute a protocol deviation as some patients will have started ADT prior to consenting on the trial
- c. Protocol therapy may last until completion of 7 cycles of therapy, unacceptable toxicity or disease progression, whichever occurs first (see [Section 5.7](#) for more comprehensive list).
- d. In the absence of toxicity, each cycle lasts 28 ± 7 days.

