12.0 ENDPOINT EVALUATION CRITERIA/MEASUREMENT OF EFFECT

12.1 Efficacy Endpoints

Response and progression will be evaluated in this study using modified Prostate Cancer Working Group 2 criteria [43] (see [Appendix C](#) and [Appendix D](#)). PSA levels will be a part of overall response assessment. Other clinical efficacy endpoints are described in [Table 12.1](#).

Table 12.1 Efficacy Endpoints

Endpoint	Definition
Time to treatment failure (TTF)	Time from the initiation of ADT for metastatic disease until PSA increase to > pre-ADT level or PSA >10 (whichever is smaller) or radiographic or clinical progression or resumption of ADT by physician's choice
Objective response rate (ORR)	Proportion of patients achieving CR or PR at Cycle 8 Day 1 (post-6 doses of radium Ra 223 dichloride)
Complete response (CR) rate	Proportion of patients achieving CR
Progression-free survival (PFS)	Time from the initiation of ADT for metastatic disease until PSA progression or radiographic progression or death
Bone specific progression-free survival (Bs-PFS)	Time to progression of bone specific disease over baseline
Duration of response (DOR)	Time from documented response to recurrent or progressive disease is first met
Duration of overall complete response	Time from documented CR to recurrent/ progressive disease
Duration of stable disease	Time from start of treatment until the criteria for progression are met, taking as reference the smallest measurements recorded since the treatment started.
Overall Survival (OS)	Date of initiation of protocol treatment to date of death from any cause

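### Table 12.1 counts PFS from ADT start but OS from the undefined start of protocol treatment, most naturally read as Cycle 1 Day 1 and at least 28 days later, so a man who dies without progression has a PFS longer than his OS.

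*Combined protocol and SAP*

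**What the plan says.** Section 12.1, Table 12.1, sets these time origins:

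- TTF (primary): "Time from the initiation of ADT for metastatic disease until PSA increase to > pre-ADT level", followed by further failure criteria.
- PFS: "Time from the initiation of ADT for metastatic disease until PSA progression or radiographic progression or death".
- OS: "Date of initiation of protocol treatment to date of death from any cause".
- Duration of stable disease: counted from a start of treatment that is not specified further.

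No section defines the start of protocol treatment. The text that bears on it is as follows.

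- Section 5.2: "Cycle 1 Day 1 is defined by the administration of SBRT".
- Section 5.3: "Participants must already have received at least 28 days of ADT" before that day.
- Section 11.0, footnote a: "Screening activities to occur within 56 days prior to Cycle 1 Day 1 of protocol therapy".
- Synopsis, Study Design: 4 weeks of ADT come first, then 32 weeks on protocol, 36 weeks in all.
- Section 3.1, inclusion 14: "The patient may join the study at any point of the 36-week period of ADT treatment".
- Table 6.1: if certain start criteria are not met and SBRT cannot begin 28 (+7) days after the first ADT dose, protocol therapy is discontinued. Men who began ADT together with radiation or surgery are excepted from the time limit.

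Section 13.5 lists PFS and OS among the secondary analyses and does not mention their origins.

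**The concern.** Death is an event for both PFS and OS. With a common origin, PFS cannot be longer than OS in the same man. Here the PFS clock appears to start at least four weeks before the OS clock, so that ordering can fail.

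Both endpoints are named secondary objectives in the same 24 evaluable patients, and readers will set the two curves and medians side by side. Those curves would be on different clocks. The offset is not the same for every man, so no single constant puts them back on one scale. A reader who subtracts one from the other to gauge survival after progression would get a figure that is too short by each man's own lead-in.

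**Working it through.** **Inputs.** The minimum lead-in is 28 days (Section 5.3). The planned split is 4 + 32 weeks (Synopsis). The Table 6.1 window is 28 + 7 = 35 days. Inclusion 14 refers to the 36-week ADT course. Cycles last 28 days, with radium on Day 1 of Cycles 2 to 7 (Section 5.2). I take a month as 30.44 days.

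**Step 1: the plan's own figure.** 28 days = 4 weeks. The 32 weeks on protocol are 8 × 28 = 224 days. The total is 28 + 224 = 252 days = 36 weeks, which agrees with the Synopsis.

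**Step 2: the offset.** Let A be ADT start, C be Cycle 1 Day 1, P be progression and D be death. Take C as the start of protocol treatment, and let g = C − A.

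- Death without progression: PFS = D − A and OS = D − C, so PFS − OS = g. This is at least 28 days.
- Death after progression: PFS = P − A and OS = D − C, so PFS exceeds OS exactly when D − P < g.

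**Step 3: size.** Take a man who dies without progression 18.0 months after ADT start, so that PFS = 18.0. This record is an illustration, not data.

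| Cycle 1 Day 1 after ADT start | g (months) | OS (months) |
|---|---|---|
| 28 days (planned lead-in) | 28/30.44 = 0.92 | 17.08 |
| 35 days (Table 6.1 window) | 35/30.44 = 1.15 | 16.85 |
| 84 days (week 12) | 84/30.44 = 2.76 | 15.24 |
| 252 days (end of ADT course) | 252/30.44 = 8.28 | 9.72 |

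**Step 4: how far along this table the plan allows.** The first two rows follow from the planned schedule and Table 6.1. The last row needs inclusion 14 to be read as letting SBRT itself start as late as the end of the ADT course.

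The week-12 row comes from the radium schedule. If Cycle 1 Day 1 is at week w, the radium doses fall at weeks w + 4 to w + 24. All six fall within the 36 weeks of ADT only if w + 24 ≤ 36, so w ≤ 12. Section 2.6 describes radium as given during ADT but does not state this as a limit. With w = 30, the doses would fall at weeks 34, 38, 42, 46, 50 and 54, five of them after ADT ends.

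**Step 5: the primary endpoint.** TTF has its own origin, ADT start. The design in Section 13.5 (24 patients, median 16 against 32 months, one-sided 10%) uses neither OS nor PFS.

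**The case against.** **The term could include ADT.** The schema footnote links the end of protocol therapy to completion of ADT. The objectives describe the protocol regimen as ADT with SBRT and radium. Table 6.1 discontinues protocol therapy before any SBRT has been given, and calls ADT after that point non-protocol. If ADT start counts as the start of protocol treatment, the offset is zero. This stands as a real ambiguity. Sections 5.2 and 5.3, the calendar and the Synopsis split favour Cycle 1 Day 1, as does the rule in Section 4.2.2 that registration precedes protocol therapy while ADT may precede consent. Either way, the term needs a definition.

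**An eight-month gap is not the expected case.** A reader might infer from inclusion 14 that gaps of up to about 8 months are generally to be expected. The documents do not support that. Inclusion 14 says when a man may join, not when SBRT may start. Table 6.1 points to 28 to 35 days and exempts only men who started ADT with radiation or surgery, although it is written as the action for an unmet criterion and not as a general limit.

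**The harm can be overstated.** A reader might also infer that time after progression is understated for every patient. OS minus PFS is not a planned analysis, it is undefined for men who have not progressed or died, and it can be computed directly from the progression and death dates. PFS includes PSA progression, so many PFS events should come well before death. Crossing curves are possible but not shown to be likely.

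**A later OS origin has merit.** Section 13.2 makes efficacy evaluability depend on SBRT and at least one radium dose. Simply moving OS back to ADT start would add time during which an evaluable man could not have died. This stands, and it shapes the fix.

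**Conclusion.** The concern holds in a limited form. As Table 12.1 is written, and with Cycle 1 Day 1 taken as the start of protocol treatment, PFS exceeds OS by at least 28 days (0.9 month) in any man who dies without progression. It also exceeds OS in any man who dies after progressing but within a time shorter than his lead-in.

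The usual gap is 28 to 35 days. A longer gap is foreseeable mainly in men who started ADT with definitive radiation or surgery, with 36 weeks (8.3 months) as an outer bound. Inclusion 14 and Table 6.1 must be reconciled before the range can be stated firmly.

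The number of men affected cannot be derived, because the documents give no expected count of deaths without progression. The problem concerns the definition and reporting of secondary endpoints. It does not touch the primary TTF test or the sample size.

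**What to change.** In Table 12.1, define the start of protocol treatment and give OS, PFS and duration of stable disease one common time origin. Then PFS ≤ OS holds for each man by construction. Two choices work:

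- **ADT start, as for TTF.** Analyse with delayed entry, so that each man joins the risk set only when he becomes evaluable under Section 13.2. Without this, the lead-in counts as guaranteed survival.
- **Cycle 1 Day 1.** Keep OS there and report PFS from the same date alongside it. Because evaluability also needs a radium dose, roughly the 28 days of Cycle 1 remain guaranteed unless delayed entry is applied here too.

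Separately, reconcile inclusion 14 with the Table 6.1 window so that the possible lead-in is clear.

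The cost is a wording change and, for delayed entry, a standard option in the survival analysis. ADT start is already needed for TTF, and Cycle 1 Day 1 is a treatment date, so no new data should be required. The downside is that the stated OS or PFS shifts by the ADT lead-in. The choice is best fixed before the data are analysed.

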12.2 Toxicity

Toxicity will be graded according to the NCI [CTCAE version 5.0](#). The highest AE grade per cycle will be reported in the eCRF from start of therapy until the end of treatment visit.

12.3 Alkaline phosphatase

Levels of alkaline phosphatase will be assessed at baseline and at the end of protocol therapy. The rate of normalization of the total alkaline phosphatase level (defined as a return to a value within the normal range) at the end of protocol therapy in patients with total alkaline phosphatase values above the upper limit of the normal range at baseline will be assessed.

13.0 STATISTICAL CONSIDERATIONS

13.1 Study Design

This multimodality Phase2study is designed to test the preliminary efficacy and to determine if androgen deprivation therapy (ADT), stereotactic body radiation therapy (SBRT) and radium Ra 223 dichloride, all delivered at the standard doses are well-tolerated in patients with oligometastatic hormone sensitive prostate cancer. The motivation behind using the standard doses for each as the starting dose is due to the limited sites of SBRT permitted in this study (≤ 4 metastatic lesion) and the prior data of radium Ra 223 dichloride when combined with ADT in a more advanced disease setting which suggest that the standard dosing should be safe and appropriate[21].

Correlative tissue studies are also incorporated into this protocol to explore the prevalence of genomic alterations in this population. Additionally, changes in immune biomarkers over the course of ADT-radiotherapy will be analyzed in an exploratory manner.

13.2 Evaluable Participants

- **Evaluable for toxicity**
 - Patients who received at least 1 SBRT dose will be evaluable for toxicity.
 - Patients who have received at least 1 dose of SBRT and at least 1 dose of Radium 223 will be evaluable for assessment of toxicity and efficacy.
- **Evaluable for response**
 - Only those patients who have evaluable disease present at baseline, have received at least one dose of SBRT and at least 1 dose of radium Ra 223 dichloride, will be considered evaluable for response.

13.3 Accrual and Expected Duration of Trial

The sample size is 24 evaluable patients (as of July 2023 we had 1 inevaluable patient, therefore we will need to accrue a total of 25 patients to get 24 evaluable patients). Accrual is expected to be completed in 66 months.

Participant duration is planned for 68 months which includes protocol therapy (~ 8 months) and follow-up (5 years).

The estimated total study duration will be 134 months (~ 11 years), with 66 months of accrual and approximately 68 months of protocol therapy and follow-up for the last patient.

13.4 Stopping Rules for Excessive Toxicity

The stopping rules for safety/toxicity will be assessed for each patient after the first 2 cycles of radium dichloride 223. The expected rate of unacceptable toxicity should not be $\geq 33\%$.

A patient will be deemed to have experienced an Unacceptable Toxicity (UT) if any of the following occur during the **first 2 cycles of radium Ra 223 dichloride (Cycles 2 and 3)** and are attributed as possibly, probably, or definitely related to protocol therapy:

- **Hematological**
 - Any \geq Grade 3 hematological toxicity that delays the next planned dose of radium Ra 223 dichloride by > 28 days

○ *Non-hematological*

- Any >Grade 2 fracture
- Any \geq Grade 3 non-hematological toxicity that does not resolve to \leq Grade 2 with adequate supportive care and delays the next planned dose of radium Ra 223 dichloride by > 28 days
- Any recurrent \geq Grade 3 toxicity

The following table will be consulted as relevant toxicities defined above are encountered.

When a stopping rule is triggered, the study PMT will review and assess the safety of the trial and submit a report to the COH DSMC. The COH DSMC will review for approval any decision to continue accrual, amend the protocol, or permanently suspend accrual to the trial.

# of patients treated that determines early stopping	# of patients with unacceptable toxicity	Given the following toxicity rates, cumulative probability of early stopping:		
		10%	25%	35%
≤ 6	2	0.11	0.47	0.68
≤ 10	3	0.14	0.56	0.80
≤ 12	4	0.14	0.58	0.81
≤ 15	5	0.14	0.59	0.83
≤ 18	6	0.14	0.60	0.85
≤ 21	7	0.14	0.61	0.86
< 24	8	0.14	0.61	0.86

13.5 Statistical Analysis Plan

With 24 evaluable patients treated we will estimate median time to treatment failure (radiographic or PSA progression, death or cessation of treatment due to clinical progression or toxicity). Our historical data suggest a 16 month median time to TTF [10]. Other studies varied in results and endpoints used, ranging from a median time to failure of 11 months [45], median distant progression free survival of 21 months [46], and median time to clinical progression of 18 months [23]. Even when permitting a lower PSA entry criteria ($PSA > 0.2$) the median time to progression was 21 months [14]. (Note: This observation has allowed us to amend this study to permit that lower PSA entry criteria to help with accrual). We seek to demonstrate a median TTF of at least 25 months, exceeding reports from all previous prior studies that examined only a two modality approach. With 24 evaluable patients, accrued over 16 months and followed for 18 months, we will have greater than 80% power to detect an improvement in TTF from 16 months to 32 months with a one-sided type I error of 10%. The critical value for a promising median TTF based on this design is 25 months, or an improvement of 9 months over our historical data. If patients experience treatment failure at ONLY an untreated asymptomatic low volume locoregional recurrence (allowed per amendment 6 based on PI discretion), TTF will be censored at that time for that patient.

Other secondary analysis will include progression-free survival, overall survival, complete response rate, duration of response, and duration of overall complete response, bone specific progression-free survival and duration of stable disease.

Exploratory analysis will include describing the rate of normalization of the total alkaline phosphatase level at the end of protocol therapy and evaluation of the role of genomic mutations and immune biomarker

studies on outcome and toxicity. These outcomes will be reported to provide further support, combined with the activity, and tolerability to help guide additional studies.

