5.6 Criteria for Removal from Protocol Therapy

Participants will receive protocol therapy until one of the following criteria are met:

- Disease progression despite castration levels of testosterone < 50 ng/dL
- Completion of 7 cycles of protocol therapy
- Participant is deemed intolerant to protocol therapy because of toxicity, despite dose modification/ delay
 - **Note:** Participants may continue to receive ADT as clinically indicated and per investigator discretion if the other study agents are discontinued.
- Withdrawal of consent for future protocol therapy (See [Section 17.5](#))
- General or specific changes in the participant's condition that render the participant unacceptable for further treatment in the opinion of the treating investigator.

Once participants meet criteria for removal from protocol therapy, the participant should then proceed to End of Treatment assessments.

Documentation of the reason for discontinuing protocol therapy and the date effective should be made in the Electronic Health Record (EHR) and appropriate eCRF.

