The same method of assessment and the same technique should be used to characterize each identified and reported lesion at baseline and during follow-up. Imaging-based evaluation is preferred to evaluation by clinical examination when both methods have been used to assess the antitumor effect of a treatment

- **Clinical lesions:**

Clinical lesions will only be considered measurable when they are superficial (e.g., skin nodules and palpable lymph nodes). In the case of skin lesions, documentation by color photography, including a ruler to estimate the size of the lesion, is recommended.

- **Chest x-ray:**

Lesions on chest x-ray are acceptable as measurable lesions when they are clearly defined and surrounded by aerated lung. However, CT is preferable.

- **Conventional CT and MRI:**

These techniques should be performed with cuts of 10 mm or less in slice thickness contiguously. Spiral CT should be performed using a 5 mm contiguous reconstruction algorithm. This applies to tumors of the chest, abdomen, and pelvis. Head and neck tumors and those of extremities usually require specific protocols

- **Ultrasound (US):**

When the primary endpoint of the study is objective response evaluation, US should not be used to measure tumor lesions. It is, however, a possible alternative to clinical measurements of superficial palpable lymph nodes, subcutaneous lesions, and thyroid nodules. US might also be useful to confirm the complete disappearance of superficial lesions usually assessed by clinical examination

- **Endoscopy, Laparoscopy:**

The utilization of these techniques for objective tumor evaluation has not yet been fully and widely validated. Their uses in this specific context require sophisticated equipment and a high level of expertise that may only be available in some centers. Therefore, the utilization of such techniques for objective tumor response should be restricted to validation purposes in reference centers. However, such techniques may be useful to confirm complete pathological response when biopsies are obtained.

- **Tumor markers:**

Baseline PSA is defined as the last known PSA prior to the onset of ADT (anti-androgen or LHRH agonist/antagonist). PSA response criteria will be a part of overall response assessment and will also be recorded as a separate PSA response criteria. They are follows:

- PSA CR - PSA <0.04 confirmed at least 3 weeks later
- PSA PR - PSA decline by >50 % from baseline, confirmed at least 3 weeks later

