- PSA SD - PSA not meeting criteria for CR, PR or PD

- PSA PD - PSA increase by $\geq 25\%$ over baseline and to at least PSA >2 ng/mL confirmed at least 3 weeks later

- **Cytology, Histology:**

These techniques can be used to differentiate between partial responses (PR) and complete responses (CR) in rare cases (e.g., residual lesions in tumor types, such as germ cell tumors, where known residual benign tumors can remain).

The cytological confirmation of the neoplastic origin of any effusion that appears or worsens during treatment when the measurable tumor has met criteria for response or stable disease is mandatory to differentiate between response or stable disease (an effusion may be a side effect of the treatment) and progressive disease.

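### Time to treatment failure, the sole primary endpoint, has two conflicting lists of failure events, and nothing says which one the 25-month criterion uses

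*Combined protocol and SAP*

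**What the plan says.** Section 13.5 (Statistical Analysis Plan) says the trial will estimate "median time to treatment failure (radiographic or PSA progression, death or cessation of treatment due to clinical progression or toxicity". The synopsis, under Statistical Considerations, repeats this. Neither place states a time origin.

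Table 12.1 defines the endpoint differently: "Time from the initiation of ADT for metastatic disease until PSA increase to > pre-ADT level or PSA >10 (whichever is smaller"; after that PSA rule it adds "radiographic or clinical progression or resumption of ADT by physician's choice". No confirmation of the PSA rise is mentioned. In the same table, progression-free survival runs "until PSA progression or radiographic progression or death".

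Appendix C defines PSA progressive disease as a rise of at least 25% "over baseline and to at least PSA >2 ng/mL confirmed at least 3 weeks later". Its reference value is also pre-treatment: "Baseline PSA is defined as the last known PSA prior to the onset of ADT".

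The design in Section 13.5 uses 24 evaluable patients, 16 months of accrual and 18 months of follow-up. It tests a median of 16 against 32 months at one-sided 10%, claims more than 80% power, and sets a critical median of 25 months.

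**The concern.** The two lists cannot both be the primary endpoint, and neither contains the other. Section 13.5 has death and toxicity stops, which Table 12.1 lacks. Table 12.1 has ADT restarts, which Section 13.5 lacks.

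The disputed events are foreseeable. Section 2.6 plans to stop ADT after 36 weeks and to restart it at recurrence. Sections 6.2 and 6.3 set out permanent discontinuation of radium for toxicity. The omission of death from Table 12.1 does not look like a convention of the table, because the progression-free survival row names it.

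This is a single-arm, open-label trial of 24 patients judged against one fixed line. If the definition is chosen after the data are seen, the conclusion could turn on that choice, and the stated 10% type I error would no longer be assured.

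**Working it through.** **1. The plan's own figure.** Assume exponential failure times and uniform accrual over 16 months plus 18 months of follow-up. The chance that a patient has an event is 1 − [exp(−18λ) − exp(−34λ)]/(16λ), with λ = ln 2/median.

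- Median 16: λ = 0.0433, probability 0.669, 24 × 0.669 = 16.1 events.
- Median 32: λ = 0.0217, probability 0.428, 24 × 0.428 = 10.3 events.

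Use the cube-root-of-hazard approximation with 10.3 events. The critical median is 16/[1 − 1.2816/(3√10.27)]³ = 16/0.651 = 24.6 months, and the power is 0.81. This agrees with the stated 25 months and more than 80%. The power calculation is not at fault.

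**2. The two definitions side by side.**

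| Component | Section 13.5 and synopsis | Table 12.1 |
|---|---|---|
| Radiographic progression | yes | yes |
| Clinical progression | as a reason for stopping treatment | yes |
| PSA | PSA progression, not defined there | above the smaller of pre-ADT level and 10 |
| Death | yes | not listed |
| Stopping for toxicity | yes | not listed |
| Restarting ADT | not listed | yes |
| Time origin | not stated | start of ADT for metastatic disease |

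**3. Toxicity stops counted or not.** The documents give no toxicity-stop rate, so the number k is an assumption. Let all other failures be exponential with median 32 months, and let k of 24 patients stop for toxicity well before the median. If the stops count, the median t solves (1 − k/24) × 0.5^(t/32) = 0.5, so t = 32 × log2[2(1 − k/24)].

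- k = 3 (12.5%): 32 × log2(1.750) = 25.8 months
- k = 4 (16.7%): 32 × log2(1.667) = 23.6 months
- k = 5 (20.8%): 32 × log2(1.583) = 21.2 months

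If they do not count, and all else is equal, the median stays at 32.

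**4. Both directions are possible.** Take a constructed set of 24 patients with complete follow-up: 10 failures evenly spaced from month 8 to 23 and 14 from month 27 to 53. The 12th failure gives a median of 29.0 months. Make two of the later patients early toxicity or death failures, counted only by Section 13.5: its median is 23.0, while Table 12.1 gives 29.0. Make two of them ADT restarts at months 20 and 20.5, counted only by Table 12.1: the order reverses, 23.0 under Table 12.1 and 29.0 under Section 13.5.

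**5. Simulation of the toxicity component alone.** The set-up was 20,000 trials of the planned design, with a true median of 32 months for other failures and toxicity stops uniform over months 1 to 9. A Kaplan-Meier median not reached was taken as at least 25.

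| Assumed share stopping for toxicity | Chance of median ≥25, stops not counted | Chance, stops counted | Same data pass one way and fail the other |
|---|---|---|---|
| 5% | 0.76 | 0.67 | 10% |
| 10% | 0.77 | 0.56 | 21% |
| 20% | 0.77 | 0.34 | 43% |

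**6. PSA, if Section 13.5 means the Appendix C rule.** For pre-ADT PSA b, Table 12.1 triggers above min(b, 10) and Appendix C at about max(1.25b, 2). The gap in doublings is log2 of the ratio.

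- b = 0.3: 0.3 against 2, 2.74 doublings
- b from 1.6 to 10: ratio 1.25 throughout, 0.32 doublings
- b = 50: 10 against 62.5, 2.64 doublings

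The documents give no PSA doubling time. At an assumed 3 to 9 months, 0.32 doublings is about 1 to 3 months and 2.74 doublings about 8 to 25 months, in an individual patient.

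**The case against.** The best defence is that Table 12.1 is the formal definition and the parenthesis in Section 13.5 is a loose summary of it. For PSA this is a fair reading. Section 13.5 does not cite Appendix C, the Appendix C categories serve response assessment, and Table 12.1 gives a PSA rule specific to this endpoint. A PSA conflict is therefore possible, not established. The defence fails for the other components: a summary would not add death and toxicity or drop ADT restarts.

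Several stronger readings are tempting, and the documents do not support them.

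- **That Table 12.1 systematically flatters the regimen.** It omits death and toxicity stops but counts ADT restarts, and possibly triggers earlier on PSA. These effects oppose each other, and no event rates are given from which to net them.
- **That the PSA difference by itself could swallow the 9-month improvement sought.** The wide gaps arise only at low or high pre-ADT values. A delay in one patient is also not a shift in the group median, because six-monthly scans or an ADT restart may come first.
- **That patients kept on ADT after radium stops escape failure under Table 12.1 and should be scored as failing at week 36.** Section 5.6 does say "Participants may continue to receive ADT as clinically indicated and per investigator discretion if the other study agents are discontinued". But neither text contains such a rule, planned ADT is only approximately 36 weeks, and nothing shows how often it would run longer. What stands is the narrower point that Table 12.1 records no failure when radium is stopped for toxicity.

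The Section 13.5 wording is itself unclear. Because other agents may continue after one is stopped, a toxicity stop could mean radium alone or all protocol therapy.

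**Conclusion.** The contradiction over death, toxicity stops and ADT restarts holds on the text alone and needs no assumption. It should be resolved before analysis, because it concerns the sole primary endpoint and the fixed criterion by which the trial is judged.

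Its numerical effect is conditional. With a 32-month median for other failures, about 4 early toxicity stops in 24 take the median below 25 months; 3 do not. Those counts, the exponential form and the early timing are assumptions. A reader might infer that this trial will pass under one text and fail under the other. The calculations show only that it can, and in either direction. The PSA component is a secondary ambiguity that rests on reading Appendix C into Section 13.5, and it is small for pre-ADT values of 1.6 to 10. The missing time origin in Section 13.5 is a gap, not a contradiction.

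**What to change.** Before analysis, write one definition in Table 12.1 and have Section 13.5 and the synopsis cite it. Build it from components the two texts already name:

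- the Table 12.1 PSA rule, stating whether the rise must be confirmed
- radiographic progression
- clinical progression
- death from any cause
- stopping treatment for toxicity, stating whether this means radium alone or all protocol therapy
- restarting ADT

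State the time origin in the same place. Report the analysis without toxicity stops as a sensitivity analysis.

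Two checks go with this. First, establish which failure definition produced the 16-month historical median, since Section 13.5 does not say and the comparison depends on it. Second, confirm that ADT restarts after the end-of-treatment visit are recorded. Footnote r of Table 11.0 ends medication recording at that visit, although the table also marks it during Response Follow-up. With ADT started 4 weeks before SBRT and no delays, the visit falls at about week 4 + 24 + 4 = 32 from the start of ADT, before the planned 36 weeks end.

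The change is to wording, plus possibly a data-capture clarification. Its cost is a shorter median, possibly materially so, and a lower chance of reaching 25 months: about 0.77 down to 0.56 in the simulation if 10% stop early for toxicity.
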